2.0 INTRODUCTION & RATIONALE

The VisAbility™ Micro Insert is a curved scleral implant that is injection molded from polymethylmethacrylate (PMMA), a material with an extensive history of use in permanent implants in the human eye, including intraocular lenses (IOLs). Four VisAbility™ Micro Inserts are placed in a single presbyopic eye to improve near vision.

Each VisAbility™ Micro Insert consists of 2 pieces, a main body segment with 2 legs and a locking segment. The locking segment has trans-longitudinal grooves on both sides that correspond to 2 small "rails" on the interior edges of the legs of the main body segment (**Figure 1**). These features allow the locking segment to be smoothly snapped into place in the main body segment. The design of the VisAbility™ Micro Inserts include stabilization feet at each end intended to fixate at the entrance and exit sites of the scleral tunnel incision, thereby preventing displacement or migration of the implanted VisAbility™ Micro Insert. The VisAbility™ Micro Inserts are provided sterile in a Tyvek® peel pouch.

Figure 1
VisAbility™ Micro Insert Showing 2 Interlocking Pieces and Stabilization Feet

Each VisAbility™ Micro Insert is implanted in a scleral tunnel approximately 4.0 mm posterior to the corneal limbus through scleral incisions centered at the 1:30, 4:30, 7:30, and 10:30 o'clock oblique quadrants. **Figure 2** shows a human eye model implanted with four VisAbility™ Micro Inserts.

[figure not shown]

FIGURE 2
PLACEMENT OF THE VISABILITY MICRO INSERTS

3.0 SUBJECT POPULATION

Subjects who participated in the VIS-2014 clinical trial.

3.1 INCLUSION CRITERIA

- Subjects must have been implanted or explanted with the VisAbility™ Micro Insert in the VIS-2014 clinical trial.
- Subjects must be alert, mentally competent, and able to understand and comply with the requirements of the clinical trial and be personally motivated to abide by the requirements and restrictions of the clinical trial.
- Subjects must provide written informed consent.

3.2 EXCLUSION CRITERIA

• Subjects who do not wish to participate or do not provide written informed consent.

4.0 INVESTIGATIONAL PROCEDURES

4.1 SUBJECT ENTRY

4.1.1 SUBJECT CONTACT

Each subject will be contacted and asked to participate in this follow-up study. Three documented attempts will be made by either regular mail, phone call, text, or email to contact each subject.

Once contacted, study staff will explain the study purpose, procedures, and responsibilities to each potential participant. Subjects who agree to participate must sign the informed consent, be able to understand the study requirements, be willing to follow study instructions, and agree to return for required follow-up visits.

If all three attempts to contact the subject are unsuccessful, a certified letter will be sent to the last known address of the subject and a copy of the certified letter will be retained at the study site. If there is no response from the subject over the course of the study, he/she will be considered not enrolled at the close of the 60-month window.

4.1.2 INFORMED CONSENT

Written informed consent will be obtained for all subjects who agree to enroll in VIS-2014-5YR. Subjects may be consented and enrolled at any time between the opening of the 36-month window and the close of the 60-month window.

4.1.3 SUBJECT REFUSAL, INABILITY TO PARTICIPATE, OR INABILITY TO CONTACT

If a subject refuses participation, or is unable to participate in the study, the reason for refusal or inability to participate will be documented. Documentation will also be retained for subjects who could not be contacted.

4.2 EXAMINATION SCHEDULE

Visit windows are calculated based on a 30-day month. The visit windows are based on the anniversary of the first VisAbility surgery. The examination schedule is as follows:

- Month 36 (+/- 60 days postoperative)
- Month 48 (+/- 60 days postoperative)
- Month 60 (+/- 60 days postoperative)

Subjects may be consented and enrolled at any time between the opening of the 36-month window and the close of the 60-month window. Visit data for subjects examined between visit windows for the 36, 48, and 60 month exam will be considered out-of-window.

Subjects who opt to have all implant segments bilaterally removed (explanted) after enrollment will be followed for 2 years post removal, up to a maximum of 5 years follow-up. Additional visits may include but are not limited to examination at day 1, week 1, month 1, and 2 annual visits, post removal.

4.3 CLINICAL PARAMETERS

The following clinical parameters will be measured:

- Near visual acuity (uncorrected, distance corrected)
- Distance visual acuity (uncorrected and best corrected)
- Intermediate visual acuity (uncorrected)
- Patient Preferred Distance
- Minimum add to 20/20
- Dynamic pupillometry
- Corneal Topography/Keratometry
- Manifest refraction
- IOP
- Slit lamp biomicroscopy
- Indirect Ophthalmoscopy
- Cup/Disc Ratio

A full description of the examination schedule and clinical parameters are referenced in Table 1.

4.4 DATA COLLECTION

Sample paper source documents will be provided by the Sponsor, Refocus Group, Inc. (Refocus) for each subject enrolled in the study and may be completed by the Investigator or Sub-Investigator at the time of the subject examination. The source documents should be completed in a clear and legible manner in black or blue ink and then signed and dated by the Investigator as indicated on the form. Any corrections will be made by drawing a single line through the incorrect entry, adding the correct entry, and then initialing and dating the corrected entry.

The information recorded on the source documents will then be entered into the electronic case report form (eCRF) in the Electronic Data Capture (EDC) System by the Investigator, Sub-Investigator, or designee. The validated database will be equivalent to that used for the VIS-2014 trial. Study data will be maintained on a secure computer with appropriate data security provisions. The original dated and signed source document will be kept in the subject's study file at the Investigator's site. Instructions for the entry of data into the EDC will be provided to the clinical sites.

4.5 STUDY COMPLETION PROCEDURES

4.5.1 SUBJECT COMPLETION

Subjects are considered to have completed the study if they have completed the 60-month exam, or the 60-month visit window has closed.

4.5.2 SUBJECT TERMINATION

Subjects may be terminated from the study if the Investigator believes that continued participation in the study may jeopardize the subject's health or welfare. Subjects may also elect to withdraw from the study at their discretion. Every effort will be made to encourage the subject to maintain compliance with the protocol and to continue in the study. Furthermore, every effort will be made in all instances to conduct examinations as determined by the Investigator to ensure the safety of the subject. The Sponsor shall be

notified promptly by the Investigator/study staff upon the termination or withdrawal of a subject by completion of the Study Exit form. Subjects who opt to have all implant segments bilaterally removed (explanted), after enrollment in VIS-2014-5YR, will be followed for 2 years post removal, up to a maximum of 5 years follow-up. Additional visits may include but are not limited to examination at day 1, week 1, month 1, and 2 annual visits, post removal.

4.5.3 SUBJECT EXIT

A subject exit form must be completed for all subjects who either complete, discontinue, are lost to follow-up, or are terminated from the study.

5.0 STATISTICAL METHODS

5.1 SUBJECT ACCOUNTABILITY

The following terms and definitions will be used for the accountability of the study population and are based on the definitions found in ANSI Z80.29, Revision 018, Section B.5.3, as modified and explained below:

- Enrolled the total number of subjects enrolled (consented) in the study.
- Discontinued Subjects (eyes) that have discontinued treatment prior to the visit window associated with the form, as a result of death, or any other reason except lost to follow-up.
- Lost to Follow-up Subjects that have withdrawn from the study after enrollment, or subjects
 that have missed the visit window associated with the form and all subsequent scheduled
 visits despite documented efforts by the Investigator to schedule the subject for follow-up.
- Missed Visit Data for subjects (primary eyes) that is not available for a follow-up visit within
 the specified visit window associated with the form, but data is available for a subsequent
 follow-up visit for such subject.

5.2 STATISTICAL ANALYSIS

Due to the observational, non-comparative nature of this study, the statistical analysis will be based on descriptive statistics. Summary statistics will be provided for all primary and secondary outcomes (listed above in Section 1.6) for primary and all eyes.

All subjects enrolled will be included in the data analyses. Visit data for subjects examined between visit windows for the 36, 48, or 60 month exam will be considered out-of-window. Missing data will only be imputed for observations that occur after enrollment into the study. In the absence of observed data between 36 months and including 60 months, the missing data will be imputed using trends seen in subjects with available data using data recorded between and including the 36-month visit up to the 60-month visit (including out of window). Scientific evidence and rational for those trends and imputation methodology will be provided in the report of the final analysis. Imputation may include but is not limited to; best/worst case analysis, multiple imputation or tipping point analysis (for binary outcomes).

Analysis will contain primary implanted eyes (dominant eye), fellow implanted eyes, and bilateral (OU) data where appropriate. Analysis will include all implanted and explanted eyes (OD, OS).

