5.3 ANALYSIS OF CLINICAL PARAMETERS

Means, standard deviations, and ranges (min/max) will be derived from the continuous measurements. Frequencies, rates (cumulative incidence), and proportions will be used for summarizing the categorical and ordinal outcomes.

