6.0 ADVERSE EVENT REPORTING

An Adverse Event (AE) is any untoward sign, symptom or disease observed during the study regardless of the suspected cause. Conditions or diseases that are pre-existing or chronic but stable are not Adverse Events. Changes in pre-existing or chronic conditions or diseases that are consistent with natural disease progression are not Adverse Events.

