6.1 SERIOUS ADVERSE EVENTS (SAE)

An Adverse Event should be classified as a Serious Adverse Event (SAE) and reported as such, if it meets one or more of the following criteria:

- It results in death (i.e., the Adverse Event causes or leads to death).
- It is life threatening (i.e., the Adverse Event places the subject at immediate risk of death).
- It is considered sight-threatening and requires intervention to prevent permanent impairment or damage.
- It requires or prolongs inpatient hospitalization. Hospitalization or prolonged hospitalization for diagnostic or elective surgical procedures for preexisting conditions are not SAEs.
- It results in persistent or significant disability/incapacity (i.e., the Adverse Event results in substantial disruption of the subject's ability to conduct normal life functions) or impairment of a body function or damage to body structures.
- It results in a congenital anomaly/birth defect in a neonate/infant born to a mother exposed to the investigational product.
- It does not meet any of the above serious criteria but may jeopardize the subject or may require medical or surgical intervention to prevent one of the outcomes listed above.

If a subject is hospitalized to undergo a medical or surgical procedure as a result of an Adverse Event, the event responsible for the procedure, not the procedure itself, should be recorded as the event. (For example, if a subject is hospitalized to undergo coronary bypass surgery, record the heart condition that necessitated the bypass).

Investigators must notify Refocus of any SAE within 24 hours of observing or learning of the event. For initial SAE reports, Investigators should record all case details that can be gathered within 48 hours on the SAE Form and fax immediately upon completion to Refocus.

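### The adverse-event reference, completion rule and accountability do not fit an enrolment period that runs from the 36-month to the 60-month window

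*Combined protocol and SAP*

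**What the plan says.** All references are to the combined protocol and SAP.

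- **Objective.** Section 1.1 seeks 36 further months of safety and effectiveness data from everyone implanted or explanted in VIS-2014.
- **Enrolment.** Under Section 4.1.2 subjects may be "consented and enrolled at any time between the opening of the 36-month window and the close of the 60-month window". Section 4.2 counts from first surgery, sets windows of 60 days either side of months 36, 48 and 60, and adds: "Visit windows are calculated based on a 30-day month". It also says: "Visit data for subjects examined between visit windows for the 36, 48, and 60 month exam will be considered out-of-window".
- **Adverse-event reference.** Section 6.0 says: "Conditions or diseases that are pre-existing or chronic but stable are not Adverse Events". It gives no date from which pre-existing is judged. Section 6.3 uses the 36-month exam. Section 6.8 compares lens opacity with the preoperative baseline and other two-grade worsening with an initial baseline of this follow-up study, which it does not define. The IOP item refers to an unspecified baseline, and the BCDVA-loss item names none.
- **Completion.** Section 4.5.1 accepts either a completed 60-month exam or closure of the 60-month window. Section 5.1 includes under lost to follow-up a subject who misses a window and all later scheduled visits despite documented efforts. Section 4.5.3 lists completion and loss to follow-up as separate exit outcomes.
- **Accountability.** Section 5.1 begins with consented subjects. Section 4.1.3 requires documentation of refusals, inability to participate and failed contact.
- **Analysis.** Section 5.2: "All subjects enrolled will be included in the data analyses" and "Missing data will only be imputed for observations that occur after enrollment into the study". Section 5.3: "Frequencies, rates (cumulative incidence), and proportions will be used for summarizing the categorical and ordinal outcomes". No time origin, risk set or denominator is given.

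**The concern.** Subjects may join at any point over more than two years, yet Section 6.3 is written as if everyone is first seen at month 36. For a later entrant the stated reference may not exist. For a subject who does attend at month 36, a stable condition that arose after VIS-2014 exit is treated as pre-existing and never becomes an adverse event, although it falls within the 36 months the study was set up to observe.

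The completion rule and the accountability list bear on how the safety results are read. If an absent subject counts as complete, the completion figure no longer describes how many were examined at five years. If the flow starts at consent, the reader cannot see how many implanted subjects are missing or whether they differed from those who returned.

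SAE rate and segment exposure are primary outcomes and AE rate is secondary (Section 1.6). The study is descriptive, so these rates are its result, and two analysts could follow Section 5.3 and divide by different numbers.

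**Working it through.** The plan states no sample size, enrolment fraction, entry pattern or event rate, so it has no figure to reproduce. The checks are window arithmetic, comparison of sections, and one conditional illustration.

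1. **Windows (Section 4.2, 30-day months, ±60 days).** Month 36: 1080 ± 60 = day 1020 to 1140. Month 48: 1440 ± 60 = day 1380 to 1500. Month 60: 1800 ± 60 = day 1740 to 1860. Consent period: 1860 − 1020 = 840 days. Part after the 36-month window closes: 1860 − 1140 = 720 days, and 720/840 = 86%. This is a share of calendar time, not of subjects.

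2. **Time hidden by the Section 6.3 reference.** Assume VIS-2014 exit at its last scheduled visit in Table 1, month 24, nominally day 720. The additional period is 1800 − 720 = 1080 days. An in-window 36-month exam falls 1020 − 720 = 300 to 1140 − 720 = 420 days after exit, which is 28% to 39% of 1080. A stable condition arising then is not an adverse event under Section 6.3. If the first exam in this study served instead (one reading of Section 6.8), the hidden time would be 1440 − 720 = 720 days (67%) for first attendance at month 48, and 1080 days (100%) at month 60. The two references coincide for a subject first seen at the 36-month exam and differ for later entrants.

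3. **Completion.** Take a subject seen at month 36 who misses months 48 and 60 despite documented efforts. After day 1860, Section 4.5.1 makes this subject complete. Under Section 5.1 no scheduled visit remains, so the subject is lost to follow-up. The Section 4.5.3 exit form treats these as alternatives. Read literally, the second limb of Section 4.5.1 is met by every subject once the window closes.

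4. **Accountability.** Section 1.1 covers all implanted or explanted subjects; Section 5.1 has no row for those who refused, were unable or were not reached. To show why this matters, suppose a fraction e enrols and the non-enrolled have k times the enrolled risk. The overall rate is then e + (1 − e)k times the enrolled rate. For e = 0.6: 0.8 (k = 0.5) to 1.8 (k = 3). For e = 0.8: 0.9 to 1.4. Both e and k are assumed, and the direction is unknown.

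5. **Denominator, conditional illustration.** Assume risk R over months 36 to 60, constant hazard, a share s entering late and evenly over that period, and only first events after entry counted. A late entrant contributes on average R/(−ln(1 − R)) − (1 − R). With R = 10%: 0.10/0.10536 − 0.90 = 4.91%. Dividing by all enrolled gives (1 − s) × 10% + s × 4.91%:
   - s = 0.10: 9.49% (5.1% too low)
   - s = 0.25: 8.73% (12.7% too low)
   - s = 0.50: 7.46% (25.4% too low)

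   If all late entrants join at month 60, the shortfall equals s. With at-risk denominators it is 0%.

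**The case against.** The strongest reply concerns the rates. A reader might infer from "All subjects enrolled will be included in the data analyses" that events will be divided by all enrolled subjects and that the reported safety rates will therefore be too low. The documents do not support this. Section 5.3 states no denominator. Section 5.1 accounts for subjects window by window, and the rule that "Missing data will only be imputed for observations that occur after enrollment into the study" fits at-risk denominators better than an all-enrolled one. Few outcomes would be exposed in any case: explantation and persisting exposure can be seen at a late first exam, and acuity, IOP, slit-lamp and fundus outcomes describe status at a visit. An SAE must be notified "within 24 hours of observing or learning of the event", so one learned of at a late first visit may still be reported. This stands, and it reduces the denominator to a point of clarification.

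A reader might also infer that the adverse-event baselines conflict throughout. They do not. A preoperative reference for lens opacity is a legitimate item-specific comparison, and the unnamed baselines for IOP and BCDVA are omissions. The conflict lies between the 36-month exam in Section 6.3 and the initial study baseline in Section 6.8, and it affects late entrants only. The loss of conditions arising between VIS-2014 exit and month 36 affects everyone.

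On completion, Section 4.5.1 can be read as an administrative end of participation and Section 5.1 as accounting per form. The separate outcomes on the exit form prevent that reading from fully reconciling them. On non-enrolment, the plan requires repeated contact attempts and documented reasons, so the counts should exist. What is missing is the commitment to report them.

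**Conclusion.** The point holds for three rules, with a fourth item as clarification.

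- **Adverse-event reference.** Section 6.3 uses an exam that late entrants may not have had and excludes stable conditions arising in the 300 to 420 days before it, 28% to 39% of the additional period. This assumes VIS-2014 exit at nominal day 720.
- **Completion.** Sections 4.5.1 and 5.1 can classify the same subject in opposite ways. The number affected is unknown.
- **Accountability.** Non-enrolled subjects are absent from Section 5.1, although the objective covers them and the records are required.
- **Denominator.** Unstated. The documents do not show that the rates are biased, and the size of any bias cannot be computed from them. The 5% to 50% shortfalls for late shares of 10% to 50% arise only under an all-enrolled denominator with pre-entry events uncounted; with at-risk or visit-specific denominators the bias from this source is zero.

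The 840 days is exact under the plan's own 30-day month. The selection and shortfall figures are illustrations on assumed inputs. The wording should be fixed before analysis.

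**What to change.** 1. **Sections 6.0, 6.3 and 6.8.** Use one adverse-event reference that exists for every subject, for example the last VIS-2014 exam, and reconcile the three sections with it. Name the baseline for the IOP and BCDVA items. The preoperative reference for lens opacity may stay, labelled as item-specific.
2. **Section 4.5.1.** Delete the limb that grants completion when the 60-month window closes, so that completion means the 60-month exam was done.
3. **Section 5.1.** Start from all VIS-2014 implanted or explanted subjects, add rows for refused, unable and not reached, and compare enrolled with non-enrolled subjects on last VIS-2014 status.
4. **Section 5.3.** State the time origin and denominator for event rates: subjects observed in each interval, not all enrolled, with contiguous intervals so that those first seen between windows have a place. Show events dated or first found between VIS-2014 exit and consent as a separate labelled count. Explantations and persisting exposure found at a late first exam should still enter the cumulative status by time since surgery; leaving them out would remove events from primary outcomes.

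The cost is wording and modest extra tables, with no new visits. Some VIS-2014 status will be missing, and completion and adverse-event figures may look less favourable.

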1.6 DATA ANALYSES

Descriptive statistics and summaries will be provided for primary eyes and all eyes for the following:

Primary safety outcomes:

- Partial explantation (1–3 Micro inserts per eye) or complete explantation (4 Micro inserts per eye) and reason(s)
- Anterior Segment Ischemia (Grades 2 4)
- Segment exposure due to conjunctival and/or scleral erosion
- Rate of serious adverse events (SAEs)

Secondary safety outcomes:

- Best Corrected Distance Visual Acuity (BCDVA)
- IOP increase > 10 mm Hg over baseline or IOP > 30 mm Hg
- Slit Lamp findings
- Fundus exam findings
- Rate of adverse events (AE's)

Secondary effectiveness outcome:

 Change in uncorrected and distance corrected near visual acuity and letters correct in the primary eye of bilaterally implanted subjects (with all eight implants in place), as compared to baseline (VIS-2014).

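### Eyes with no segment left at the start of the extension count in the denominators for segment exposure and explantation, which lowers any rate counted within the extension

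*Combined protocol and SAP*

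**What the plan says.** Eligibility (Section 3.1) covers people explanted in the parent trial as well as those still implanted: "Subjects must have been implanted or explanted with the VisAbility™ Micro Insert in the VIS-2014 clinical trial". Section 5.2 sets the analysis population: "All subjects enrolled will be included in the data analyses". It applies that population to the outcomes, "Summary statistics will be provided for all primary and secondary outcomes (listed above in Section 1.6) for primary and all eyes", and closes with "Analysis will include all implanted and explanted eyes (OD, OS".

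Two of the primary safety outcomes in Section 1.6 depend on an insert being present:
- "Segment exposure due to conjunctival and/or scleral erosion"
- "Partial explantation (1–3 Micro inserts per eye) or complete explantation (4 Micro inserts per eye) and reason(s"

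Neither has a denominator of its own. The only restriction by implant status in Section 1.6 is on the secondary effectiveness outcome, which is assessed "in the primary eye of bilaterally implanted subjects (with all eight implants in place" at the time.

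On the measure, Section 5.3 says: "Frequencies, rates (cumulative incidence), and proportions will be used for summarizing the categorical and ordinal outcomes". It names neither the date from which incidence accumulates nor the eyes at risk.

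**The concern.** Segment exposure and explantation are events of the device in the eye. An eye from which all four inserts were removed before the extension began cannot have either event afterwards. Under the general inclusion rule it is still counted among the eyes observed. The extension-period rate then mixes eyes that could have the event with eyes that could not, and always reads lower than the rate among eyes that still carry the device.

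The study exists to describe long-term safety, and these are two of its four primary safety outcomes. The error is in the device's favour. A reader who wants to know how often a retained implant becomes exposed or has to be removed in years three to five would be given too small a figure.

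**Working it through.** **Inputs from the documents.** Explanted subjects are eligible (Sections 1.1, 1.3 and 3.1). All enrolled subjects and all implanted and explanted eyes are analysed (Section 5.2). Exposure and explantation carry no at-risk restriction (Section 1.6). The documents state no sample size, event rate or number of explanted eyes, so there is no figure of the plan's own to reproduce.

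**Assumed inputs.** Let f be the share of analysed eyes with no segment at the start of the extension, and r the rate among eyes with at least one segment. I take r = 4% and f = 5%, 10% and 20%, with 400 eyes where a count is needed. All of these are illustrations.

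**Step 1: the identity.** With N eyes, N(1 − f) are at risk and the events number N(1 − f)r. Dividing by all N eyes gives r(1 − f). The relative understatement is 1 − r(1 − f)/r = f, whatever r is.

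**Step 2: the numbers.**

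| f | Eyes at risk of 400 | Events at r = 4% | Rate on all eyes | Rate on eyes at risk |
|---|---|---|---|---|
| 5% | 380 | 15.2 | 15.2/400 = 3.8% | 4.0% |
| 10% | 360 | 14.4 | 14.4/400 = 3.6% | 4.0% |
| 20% | 320 | 12.8 | 12.8/400 = 3.2% | 4.0% |

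The same identity holds for the primary-eye summaries, with f taken as the share among primary eyes.

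**Step 3: no events seen.** The one-sided 95% upper bound is 1 − 0.05^(1/n). On all 400 eyes it is 0.75%. On the 380, 360 or 320 eyes at risk it is 0.79%, 0.83% or 0.93%. Eyes that cannot have the event make the bound look tighter than the data support.

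**Step 4: counting from first surgery.** If explantation is counted from first surgery, the earlier complete removals are themselves events. The proportion is f + (1 − f)r. At f = 10% and r = 4% that is 0.10 + 0.90 × 0.04 = 13.6%. Those eyes belong in the denominator, and including them dilutes nothing.

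**Step 5: which period does the plan mean?** Section 5.3 does not say. Three places lean towards the extension. Section 1.1 aims at a further 36 months of data. Section 6.0 defines adverse events as those observed during the study. Section 6.3 excludes stable conditions already present at the 36-month exam. Section 6.8 lists segment removal and exposed segments among the possible adverse events, so these counting rules reach them. On the other side, visits are timed from first surgery (Sections 1.4 and 4.2), and Table 1 spans the whole five years.

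**The case against.** The strongest reply is that the plan never writes down a denominator for these two outcomes. The sentence on implanted and explanted eyes can be read as a statement of scope: a safety study does not drop explanted eyes. Section 1.6 shows that the sponsor does restrict by implant status where it sees a need. It is true that the denominator is inferred from the general rule. But that rule is applied to all primary outcomes and no exception is made for these two, so an analyst who follows the text would include the eyes. The category of discontinued eyes in Section 5.1 is an accountability term, and nothing says that it removes explanted eyes from outcome denominators.

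A second reply is that cumulative incidence may run from first surgery. For explantation this would remove the dilution, as Step 4 shows. It stands as a limit on the point, because the plan leaves the origin open.

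A third reply is that little turns on it. The study is descriptive, with no test or performance target, and the assumed cases differ by 0.2 to 0.8 percentage points. If the explantation table also covers removals in VIS-2014, a careful reader could rebuild the at-risk denominator. This stands as to size, though a primary safety rate should not need rebuilding.

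A reader might also infer that eyes fully explanted during the extension should leave its denominator. That does not follow. They were at risk when the period began and belong in its starting denominator. Only a later per-visit exposure rate is diluted by them.

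**Conclusion.** The point holds for rates of segment exposure and explantation counted within the extension. If the inclusion rule in Section 5.2 is followed as written, those rates are too low by the relative share of eyes with no segment at the start. The direction is certain whenever there is at least one such eye and any event occurs. The size is unknown because no explant count is given: 3.8%, 3.6% or 3.2% in place of 4% rests on assumed shares of 5%, 10% and 20% and an assumed rate, and the effect is small if few eyes were fully explanted.

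A reader might infer that every rate in the report will be biased, including five-year cumulative figures. The documents do not support that. Explantation since first surgery is not diluted, the effectiveness outcome is already restricted, and anterior segment ischemia and serious adverse events can still occur in an eye without inserts. Whether a five-year figure depends on who consents to the extension is a separate question about the enrolled sample and forms no part of this point.

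**What to change.** In Section 5.2, state the counting period for segment exposure and explantation, including the date that counts as the start of the extension, and the denominator that goes with it:

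- **During the extension:** eyes with at least one segment in place at its start. Partly explanted eyes stay in.
- **Exposure rates by visit:** eyes with at least one segment in place at that visit.
- **Eyes fully explanted during the extension:** keep them in the starting denominator, count the removal as the explantation event, and treat it as a competing event for exposure.
- **Rates since first surgery, if also reported:** label them as such and keep explanted eyes in.
- **Anterior segment ischemia, SAE, BCDVA, IOP and AE summaries:** keep fully explanted eyes in and show them in a separate row.

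The cost is a change of wording and one extra table. Table 1 already schedules an implant assessment at months 36, 48 and 60, and Appendix 1 has it record missing and exposed segments, so no new examination is needed. The extension-period rates will look slightly less favourable.
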